10.2. Analysis Populations

Three (3) analysis populations are planned for the study as follows:

- The Safety Population consists of all subjects who receive at least 1 dose of study treatment (KZR-261) and will be used for the safety analyses.
- The Response Evaluable Population is defined as all subjects who receive at least 1 dose of study treatment (KZR-261) and who have a baseline and at least 1 post-baseline anti-tumor response assessment using RECIST v1.1.
- The PK Analysis Population consists of all subjects who receive at least 1 dose of KZR-261 and who have at least one post-dose PK sample with measurable concentration of KZR-261. Any protocol deviations affecting PK analyses may result in exclusion from summaries for individual time point concentrations, complete profiles, and/or PK parameters. These exclusions will be reviewed before database lock and confirmed with the Sponsor before implementation.

Unless otherwise specified, all data will be summarized by dose level and overall for Part 1 (Dose Escalation), tumor-specific cohort for Part 2A (Dose Expansion), and dose and tumor-specific cohort for Part 2B (Dose Optimization).

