10.5.4. Safety Analysis

Safety analyses will be performed for all subjects who received at least 1 dose of study drug.

Prior and concomitant medications will be coded using the WHO Drug dictionary (version March 2023 or later). Verbatim AE terms will be coded using the Medical Dictionary for Regulatory Activities (MedDRA) (version 26.0 or later). All AEs that occur after administration of the first dose of study drug and through 30 days after last dose of study drug will be considered treatment-emergent adverse events and will be summarized by MedDRA system organ class and preferred term. The incidences (percentages) of subjects experiencing each AE preferred term will be summarized. AEs will also be summarized by severity in accordance with NCI CTCAE v5.0 and by causality (relationship to study treatment). DLTs, AEs, Grade 3, Grade 4, and Grade 5 AEs, SAEs, and AEs resulting in dose reductions, treatment interruptions, or treatment discontinuation will be summarized by MedDRA preferred terms. Deaths that occur after the first dose of study drug and through 30 days after the last dose of study drug will be considered “on treatment” deaths and will be summarized. All deaths will be listed.

Clinical laboratory, vital sign measurements, and ECG data will be summarized descriptively (means, medians, standard deviations, and minimum and maximum values) by dose/treatment group and overall and at protocol-specified time points along with a summary of change from baseline at each protocol-specified time point.

Incidence of clinical laboratory abnormalities will be summarized with descriptive statistics. Vital signs and physical examination results will be summarized with descriptive statistics. Changes from baseline in physical and ocular examination findings will be listed and described for each subject.

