### **7.4. Data Analysis Conventions**

All data analysis will be performed by [REDACTED] after the study is completed and the database has been locked. Statistical programming and analyses will be performed using SAS® version 9.4 or higher. Output will be provided in rich text format (RTF) for tables and portable document format (PDF) for tables, listings, and figures using landscape orientation. All study data will be listed by subject, dose level in Part 1 (Dose Escalation) and cohort in Part 2A and 2B (Tumor-Specific Dose Expansion and Dose Optimization), and visit (as applicable) based on all enrolled subjects unless otherwise specified. Listings will be sorted by dose level in Part 1 (Dose Escalation) and by cohort in Part 2A (Tumor-Specific Dose Expansion) and Part 2B (Dose Optimization), subject number, visit/time point, and parameter as applicable.

Summaries for continuous and ordinal variables will include the number of observations (n), arithmetic mean, standard deviation, median, minimum, and maximum. Minima and maxima will be reported with the same precision as the raw values; means and medians will be presented to one additional decimal place than reported in the raw values. Standard deviations will be presented to two additional decimal places than reported in the raw values. Summaries for discrete variables will include counts and percentages. All percentages will be rounded to one decimal place (ie, XX.X%). Changes from baseline will be calculated as follow-up visit minus baseline.

Unless otherwise specified, all data will be summarized by dose level and overall, for Part 1 (Dose Escalation), tumor-specific cohort for Part 2A (Dose Expansion), and dose and tumor-specific cohort for Part 2B (Dose Optimization).

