An overall summary that includes the number and percentage of subjects who experienced at least one TEAE, including treatment-related TEAEs, SAEs, treatment-related SAEs, TEAEs leading to treatment interruption, dose reduction, discontinuation, death, and Grade 3 or 4 TEAEs will be provided. TEAEs will be summarized by dose level in Part 1 (Dose Escalation) and by tumor cohort in Parts 2A and 2B (Tumor-Specific Dose Expansion and Dose Optimization) All verbatim TEAEs will be coded to a MedDRA system organ class (SOC) and preferred term (PT). If a subject reports the same PT multiple times within a SOC, that PT will be counted once (at the highest level of severity) within that SOC. If a subject reports multiple different PTs within the same SOC, a subject will be counted once at the SOC level. SOCs and PTs will be listed in order of descending frequency within each SOC.

Summaries of TEAEs by maximal severity will be presented.

All AEs will be presented in a subject listing.

The following will be presented as listings and summary tables:

- TEAEs leading to study treatment discontinuation
- TEAEs related to KZR-261
- TESAEs
- TESAEs related to KZR-261
- TEAEs related to KZR-261 leading to early treatment discontinuation
- TEAEs leading to dose reduction
- TEAEs leading to death by category (Death on-treatment, Death post-treatment, and all death)
- TEAEs related to KZR-261 leading to death
- Grade 3 or 4 TEAEs
- Grade 3 or 4 TEAEs related to KZR-261
- Selected TEAEs by category (such as neutropenia and neutrophil count decreased, QTc prolongation and cardiac toxicities, liver toxicity, nephrotoxicity, bone marrow toxicity, etc)

In addition, all SAEs will be presented in a separate listing.

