## **15.3. Vital Signs, Oxygen Saturation, Height, Weight**

Vital signs, including temperature (°C), systolic and diastolic blood pressure (mmHg), heart rate (bpm), and respiratory rate will be summarized using descriptive statistics, at baseline and each study day and time point by dose level in Part 1 and by tumor cohort in Parts 2A and 2B for all actively treated subjects. Oxygen saturations (%), height (cm), weight (kg), BMI (kg/m^2), and BSA (m^2) will be summarized similarly.

The following vital signs categories will also be summarized:

- Systolic pressure: for high values  $\geq 180$  and increase from baseline of  $\geq 20$ . Low values  $\leq 90$  and decrease from baseline of  $\geq 20$ .
- Diastolic pressure: for high values  $\geq 105$  and increased from baseline of  $\geq 15$ . Low values  $\leq 50$  and decrease from baseline of  $\geq 15$ .

- Heart rate: for high values  $\geq 100$  and increase from baseline of  $>25\%$ . For low values:  $\leq 50$  and decrease from baseline of  $>25\%$ .
- Body temperature: for high values  $\geq 39.1$  Celsius.

Changes from baseline will also be summarized at each post-baseline study visit.

Listings of vital signs results, oxygen saturations, height, weight, BMI, and BSA will also be produced.

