## 15.4. Electrocardiogram

QT interval corrected for pulse rate by Fridericia's formula (QTcF) will be summarized using descriptive statistics at baseline and each day and time point by dose level in Part 1 (Dose escalation) and by cohort in Parts 2A and 2B (Tumor-specific Dose Expansion and Dose optimization). Shifts from baseline in ECG interpretation will be also summarized using frequency and percentages by dose level in Part 1 (Dose Escalation) and by cohort in Parts 2A and 2B (Tumor-Specific Dose Expansion and Dose Optimization).

To assess the frequency of QTc interval prolongation, the number and percentage of subjects having notable ECG values according to the following categories will also be summarized by dose level in Part 1 (Dose escalation) and by cohort in Parts 2A and 2B (Tumor-specific Dose Expansion and Dose optimization):

- Change from Baseline in QTcF:  $\leq 30$ ,  $>30$  to  $\leq 60$ ,  $>60$  msec
- Maximal QTcF:  $>450$  to  $\leq 480$ ,  $>480$  to  $\leq 500$ ,  $>500$  msec

A subject listing of ECG data will also be produced.

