## 15.5. Clinical Laboratory Data

Continuous variables will be summarized by dose level in Part 1 (Dose Escalation) and by tumor cohort in Parts 2A and 2B (Tumor-Specific Dose Expansion and Dose Optimization) and for all actively treated subjects at each visit and time point (where appropriate) using arithmetic means, medians, minimum and maximum values. Categorical variables will be summarized by dose level in Part 1 (Dose Escalation) and by cohort in Parts 2A and 2B (Tumor-Specific Dose Expansion and Dose Optimization) using frequencies and percentages for all actively treated subjects at each visit and time point (where appropriate). Shift tables summarizing changes from baseline will also be produced by dose level in Part 1 (Dose Escalation) and by cohort in Parts 2A and 2B (Tumor-Specific Dose Expansion and Dose Optimization).

Unscheduled laboratory data will be included in subject listings and denoted as unscheduled. Summaries by visit will use the nominal visit value in the event of multiple laboratory values drawn within a visit window. However, all values drawn within a study window will be used to identify the minimal and maximal values. In the event that visit windows overlap, only the values from assessments occurring after the previous and prior to the subsequent nominal visit value will be considered for identification of the minimal and maximal values.

Summaries of abnormal laboratory results will be presented by analyte and severity grade.

A shift table consisting of changes from baseline in neutrophil counts will be produced.

A listing of tumor marker data will be produced. The tumor marker reference ranges are provided in [Appendix C Tumor Marker Reference Ranges](#).

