## **19. CHANGES FROM PROTOCOL-STATED ANALYSES**

There are no changes from the protocol-stated analyses.

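### SAP 15.1, 15.3 to 15.5 and the 13.2.7 summary group Part 2B by tumor cohort without dose, so the main safety tables merge the two randomized doses

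*SAP*

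**What the plan says.** SAP 3.1 randomizes about 30 subjects in each Part 2B tumor cohort 1:1 to the MTD/MAD or a lower clinically active dose. SAP 5 gives 15 subjects per dose level, in up to 4 cohorts.

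The general grouping rule is in Protocol 10.2, "tumor-specific cohort for Part 2A (Dose Expansion), and dose and tumor-specific cohort for Part 2B (Dose Optimization", and is repeated in SAP 7.4, "and dose and tumor-specific cohort for Part 2B (Dose Optimization". Both rules are conditional: they apply unless a section specifies otherwise. Protocol 10.5.4 separately calls for laboratory, vital sign and ECG summaries "by dose/treatment group and overall and at protocol-specified time points".

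The SAP's safety sections then set their own grouping:

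- 15.1, adverse events: "TEAEs will be summarized by dose level in Part 1 (Dose Escalation) and by tumor cohort in Parts 2A and 2B".
- 15.3, vital signs: "by dose level in Part 1 and by tumor cohort in Parts 2A and 2B for all actively treated subjects".
- 15.4, ECG: "by dose level in Part 1 (Dose escalation) and by cohort in Parts 2A and 2B".
- 15.5, laboratory data: "by dose level in Part 1 (Dose Escalation) and by tumor cohort in Parts 2A and 2B".

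The descriptive summary of best percentage change in target lesions (SAP 13.2.7) follows the same pattern: dose level for Part 1, tumor cohort for Parts 2A and 2B.

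SAP 4.3 describes a study in which every subject receives KZR-261 without being randomized, and SAP 4.2.2 gives no allocation step for Part 2B. SAP 19 states: "There are no changes from the protocol-stated analyses".

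**The concern.** In Part 2A every subject in a tumor cohort is meant to start at the same dose, so tumor cohort is a sufficient grouping. In Part 2B it is not, because each cohort contains two randomized arms that differ in dose. A safety table by tumor cohort alone adds the arms together and hides the contrast for which the subjects were randomized.

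The primary objective of Part 2 is to characterize safety and identify the RP2D (SAP 2.1.2). Adverse events, laboratory values, ECG and vital signs are primary endpoints for that objective (SAP 2.2.1.2). The affected tables are therefore those a reader would go to first when asking whether the lower dose is better tolerated.

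**Working it through.** **1. The plan's own figure.** Up to 4 cohorts × 2 dose levels × 15 subjects = 120, which matches the Part 2B maximum in SAP 5. Each cohort holds 2 × 15 = 30 subjects in two arms.

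**2. Which rule governs each output in Part 2B.**

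| Output | Grouping in its own section | Grouping that results |
|---|---|---|
| Adverse events (15.1) | tumor cohort | doses merged |
| Vital signs (15.3) | tumor cohort | doses merged |
| ECG (15.4) | cohort | doses merged |
| Laboratory (15.5) | tumor cohort or cohort | doses merged |
| Best % change, descriptive summary (13.2.7) | tumor cohort | doses merged |
| Exposure (11.2), slit lamp and visual acuity (15.2), ORR (13.2.1), CBR (13.2.5) | none stated | 7.4 default, by dose and tumor cohort |
| Waterfall plot and E-max curve (13.2.7) | dose carried | dose visible |
| Kaplan-Meier plots (13.2.2 to 13.2.4) | one set per study part | split by dose within Part 2B not stated |

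The word cohort in 15.4 and in parts of 15.5 has the same effect as tumor cohort, because Protocol 3.4 randomizes within each Part 2B cohort. Since the 7.4 rule yields to any section that specifies its own grouping, the first five rows lose the dose split.

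**3. What a merged column can hide.** The documents give no expected event rates, so the counts below are assumed. Take a merged column with 9/30 = 30% of subjects having a Grade 3 or 4 event. For each split, the 95% interval for the difference uses Newcombe's method. With Wilson limits (l, u) for each arm and d = p1 − p2:

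- lower = d − √[(p1 − l1)² + (u2 − p2)²]
- upper = d + √[(u1 − p1)² + (p2 − l2)²]

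| Split (n = 15 each) | p1 (Wilson), % | p2 (Wilson), % | d, points | 95% CI, points | Merged |
|---|---|---|---|---|---|
| 5 vs 4 | 33.3 (15.2 to 58.3) | 26.7 (10.9 to 52.0) | 6.7 | −24.5 to 36.2 | 9/30 |
| 6 vs 3 | 40.0 (19.8 to 64.3) | 20.0 (7.0 to 45.2) | 20.0 | −12.3 to 47.5 | 9/30 |
| 9 vs 0 | 60.0 (35.7 to 80.2) | 0.0 (0.0 to 20.4) | 60.0 | 28.3 to 80.2 | 9/30 |

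All three print as the same 30%.

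**4. Precision if cohorts were also displayed together.** This concerns an optional addition and does not measure the defect. Assume rates of 40% and 20% in every tumor type and the same two doses in every cohort. The 95% half-width is 1.96 × √(0.4 × 0.6/n + 0.2 × 0.8/n), which gives 32.0, 22.6, 18.5 and 16.0 points for n = 15, 30, 45 and 60 per dose (1 to 4 cohorts). Over other 20-point contrasts, from 30% vs 10% to 60% vs 40%, the half-width is 27.7 to 35.1 points at n = 15 and 13.9 to 17.5 points at n = 60.

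**The case against.** The strongest defense is that the safety sections use shorthand to cover Parts 2A and 2B together, and never say that doses are pooled. SAP 7.4 names dose for Part 2B, and a careful programmer might apply it. That reading is possible, but the default gives way to a specific instruction, and five sections give one. Each names dose for Part 1 and not for Part 2B.

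SAP 1 says that SAP methods supersede those in the protocol, so differing from Protocol 10.2 or 10.5.4 is not in itself an error. This is correct. What remains is the SAP's conflict with its own general rule and an undeclared change under SAP 19.

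The harm is bounded, and these points stand:

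- Assigned dose is listed for every subject (SAP 8), and SAP 1 allows supplementary analyses, so by-dose tables could be produced later from the same database.
- No formal dose comparison is planned in Part 2B. The RP2D rests on all Phase 1 results, and the Safety Review Committee monitors Part 2 as it runs.
- Part 2B opens only at the sponsor's discretion.
- With 15 subjects per dose, only an extreme split such as 9 vs 0 is clearly distinguishable.
- The Kaplan-Meier wording can be read as inheriting the 7.4 default, and SAP 4.3 and 4.2.2 drive no analysis. Both need clarification only.

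None of this supports merging the arms. Low precision calls for cautious reading of two columns, and a table that has to be requested afterwards is no longer the prespecified one.

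**Conclusion.** The concern holds and should be fixed. As written, the Part 2B tables for adverse events, vital signs, ECG and laboratory data, and the target-lesion summary, do not show the two randomized doses separately. This conflicts with SAP 7.4 and Protocol 10.2, and for the laboratory, vital sign and ECG data also with Protocol 10.5.4. SAP 19 does not declare it. SAP 4.3 contradicts SAP 3.1 on whether there is any randomization.

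On the assumed counts, one merged figure of 30% is compatible with dose differences anywhere from 7 to 60 points. That range illustrates the loss and does not predict the result. The conclusion about grouping rests on the wording alone and needs no assumed rate. It matters only if Part 2B is opened, and dose remains available in the listings and in the outputs that keep the default.

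**What to change.** - **Main change.** In SAP 15.1, 15.3, 15.4, 15.5 and the descriptive summary in 13.2.7, set the Part 2B grouping to randomized dose and tumor cohort, in line with SAP 7.4 and Protocol 10.2. Part 2A can stay by tumor cohort.
- **Clarifications.** State in 13.2.2 to 13.2.4 that the Part 2B Kaplan-Meier curves are shown by dose. Rewrite SAP 4.3 and 4.2.2 to describe the 1:1 Part 2B randomization given in SAP 3.1. With these edits SAP 19 can stand on this point.
- **Optional.** Add one descriptive by-dose safety display across tumor cohorts, stratified by tumor type, only if the cohorts share the same two doses.

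The cost is SAP and table-shell wording and more columns: two of about 15 subjects per cohort in place of one of about 30, so at most 8 columns instead of 4. No subjects, visits or procedures are added.

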30. Unable to comply with the protocol in the Investigator's or Sponsor's opinion.

STATISTICAL METHODS

A detailed Statistical Analysis Plan will be prepared by the Sponsor and finalized prior to database lock.

Sample Size Estimates

Approximately 70 subjects will be enrolled and treated with KZR-261 in Part 1 (Dose Escalation) in an “i3+3” design.

In Part 2A (Dose Expansion), up to 175 subjects will be enrolled based on interim futility analyses for up to 4 tumor-specific expansion cohorts and 1 All-Tumors cohort. The tumor-specific cohorts ($n = 15$ at interim) may be increased up to 35 subjects per cohort to more precisely estimate the anti-tumor activity of KZR-261, if there is a sufficient efficacy signal in the interim analyses and if the tumor type is not selected for investigation in Part 2B (dose optimization). Note: Outcomes (ie, presence or absence of clinical benefit) for subjects enrolled in Part 1 with the same tumor type and who received the same dose of KZR-261 as evaluated in the corresponding Part 2A, tumor-specific cohort may be included among the initial 15 subjects at the interim analysis.

The All-Tumors cohort may enroll up to 35 biopsy-evaluable subjects. In Part 2B (Dose Optimization), up to 120 subjects (~30 per tumor-specific cohort) may be enrolled.

Planned Statistical Analyses

Safety

Summaries and descriptive statistics will be generated for all safety data including DLTs, AEs, Grade 3, Grade 4, and Grade 5 AEs, SAEs, AEs resulting in dosing reductions, treatment interruptions, or treatment discontinuations, clinical laboratory data, vital signs, ECGs, and results of physical and ocular examinations. Deaths that occur after the first dose of study drug and through 30 days after the last dose of study drug will be considered “on treatment” deaths and will be summarized. All deaths will be listed.

Anti-tumor Activity

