9. ADVERSE EVENTS AND SERIOUS ADVERSE EVENTS

9.1. Adverse Event Reporting

9.1.1. Definitions

An AE is defined as any untoward medical occurrence in a clinical study subject administered a medicinal product, which does not necessarily have a causal relationship with this treatment. An AE can therefore be any unfavorable and unintended sign (including an abnormal laboratory finding), symptom, disease, or medical condition temporally associated with the use of a medicinal (investigational) product, whether or not it is related to the medicinal (investigational) product. This includes an exacerbation of pre-existing conditions or events, intercurrent illnesses, or drug interaction. Anticipated fluctuations of pre-existing conditions, including the disease under study, that do not represent a clinically significant exacerbation or worsening need not be considered AEs.

Progression of the underlying malignancy that is clearly consistent with the progression as defined by RECIST v1.1 criteria (or PCWG3 criteria in the setting of mCRPC), or other protocol defined criteria, is not considered an AE. Hospitalization due solely to progression of the underlying malignancy should not be reported as an SAE.

If signs, symptoms and/or physical findings cannot be determined as exclusively due to progression of the underlying malignancy or do not fit the expected pattern of progression, these clinical symptoms should be reported as AEs or SAEs.

If there is any uncertainty regarding an AE or SAE being due to progression of malignancy, these should be reported as AEs or SAEs.

Signs and symptoms associated with overdose of KZR-261 must be reported as AEs.

It is the responsibility of the Investigator to document all AEs that occur during the study. AEs will be elicited by asking the subject a nonleading question, for example, "Have you experienced any new or changed symptoms since we last asked/since your last visit?" AEs should be reported on the appropriate page of the eCRF.

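### SAP 15.1 counts deaths only through TEAEs, so it does not deliver the all-cause on-treatment death summary that Protocol 10.5.4 promises

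*SAP*

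**What the plan says.** **Endpoint.** Protocol 2.2.1.1 and 2.2.1.2, repeated in SAP 2.2.1.1 and 2.2.1.2, name deaths among the primary safety endpoints, as an item separate from AEs and SAEs.

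**Protocol rule.** Protocol 10.5.4, like the synopsis, classes "Deaths that occur after the first dose of study drug and through 30 days after the last dose of study drug" as on-treatment, and continues "deaths and will be summarized. All deaths will be listed". The rule uses dates only. Cause plays no part.

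**What counts as an AE.** Under Protocol 9.1.1, progression clearly consistent with RECIST v1.1, PCWG3 "or other protocol defined criteria, is not considered an AE". The same section sends uncertain or off-pattern cases to AE or SAE reporting. SAP 15.1 agrees: worsening of the indication is an AE only if it is not already recorded under the efficacy assessments. A TEAE must fall between the first dose and 30 days after the last.

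**SAP death outputs.** SAP 15.1 has three, all built on TEAEs: the death line in the overall summary ("TEAEs leading to treatment interruption, dose reduction, discontinuation, death, and Grade 3 or 4 TEAEs will be provided"), the item "TEAEs leading to death by category (Death on-treatment, Death post-treatment, and all death", and the drug-related subset of the latter.

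**Status.** SAP 1 says that the SAP's methods supersede the protocol's. SAP 19 says: "There are no changes from the protocol-stated analyses".

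**The concern.** The protocol's death count is neutral as to cause; the SAP's is not. Whether an early death in advanced cancer is attributed to progression or to toxicity is the investigator's judgment, here in an open-label, first-in-human trial. A count by date guards against misattribution because it needs no attribution at all. A count that starts from TEAEs loses that protection, and it does so under a category label that tells the reader every death is included.

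At stake is the final safety summary and, through it, the RP2D, which Protocol 3.2.4 bases on benefit-risk across all Phase 1 results. If one dose had more early deaths attributed to progression, no death table in SAP Section 15 would show it.

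**Working it through.** There is no figure in the plan to reproduce, so the check applies both rules to constructed records and then looks for another output that fills the gap. The SAP does not define its on-treatment category, so the protocol's 30-day boundary is used for it.

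**1. The same records under both rules** (1 = counted, 0 = not)

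| Record | Protocol 10.5.4 on-treatment summary | Protocol 10.5.4 listing | SAP 15.1 on-treatment | SAP 15.1 post-treatment | SAP 15.1 all death |
|---|---|---|---|---|---|
| A. Clear progression, death 20 days after last dose | 1 | 1 | 0 | 0 | 0 |
| B. Fatal treatment-emergent sepsis, death 20 days after last dose | 1 | 1 | 1 | 0 | 1 |
| C. Progression uncertain, reported as an SAE, death 20 days after last dose | 1 | 1 | 1 | 0 | 1 |
| D. Fatal event starting more than 30 days after last dose | 0 | 1 | 0 | 0 | 0 |
| E. Clear progression, death 5 months after last dose | 0 | 1 | 0 | 0 | 0 |

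Record A is the departure from the promised summary: 3 on-treatment deaths under the protocol, 2 under the SAP. Records A, D and E show that the all-death category is mislabelled: 5 deaths occurred and it holds 2. The records show how each type of death is classified, not how often it occurs.

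**2. Does another output supply the summary?**

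- *Overall survival (SAP 13.2.4)* counts death from any cause, but SAP 13 confines efficacy analyses to the Response Evaluable Population, which needs a post-baseline response assessment (SAP 6.2). The first scheduled imaging is at the end of Cycle 2 (Protocol 7.2.10), that is 2 × 28 = 56 days, with a 7-day window. Subjects who die before any assessment are left out, and their deaths are likely to be on-treatment deaths. There is also no on-treatment split.
- *Disposition (SAP 8)* gives reasons for leaving treatment and study, with dates in a listing. It applies no 30-day window.
- *General listings (SAP 7.4)* cover all study data for all enrolled subjects. That probably yields a death listing, but not a summary.

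**3. Breakdown in Part 2B.** SAP 15.1 summarizes TEAEs in Part 2B by tumor cohort without naming dose, whereas the default in SAP 7.4 is dose and tumor cohort. Even the AE deaths may therefore not be shown by randomized dose.

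**4. Size.** Let D be the number of on-treatment deaths and f the share attributed to clear progression and not reported as an AE. The SAP table shows D × (1 − f). The documents give neither quantity. With D = 10, assumed only for illustration:

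- f = 20%: 10 × 0.8 = 8 shown
- f = 50%: 10 × 0.5 = 5 shown
- f = 80%: 10 × 0.2 = 2 shown

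**The case against.** The best defence is that the SAP is silent rather than contrary. It states no rule against counting deaths from all causes, it declares no change, and its category labels suggest that all deaths may have been meant. On that reading Protocol 10.5.4 still applies and the SAP needs only a clarification. Deaths would also be visible elsewhere: death is an end-of-study event (Protocol 8.3.2), disposition reports reasons and dates, and the general listings cover every subject.

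Part of this stands. A listing of all deaths is largely covered by SAP 7.4, and timing could be traced by hand from the listings. But the item in SAP 15.1 is headed by TEAEs, and a programmer who follows it will produce TEAE deaths. None of the other outputs gives a Safety Population count of on-treatment deaths.

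The following stronger readings are tempting, but the documents do not support them:

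- *The protocol promises a summary of all deaths.* It promises a summary of on-treatment deaths and a listing of the rest. The all-death category is the SAP's own.
- *Every progression death is lost.* Protocol 9.1.1 routes uncertain and off-pattern cases to AE or SAE reporting, and Protocol 8.1.1 envisages a Grade 5 event that is a complication of progression. Only clear progression drops out.
- *The MTD or MAD is distorted.* The MTD and MAD definitions use DLT rates, events related to the disease are excluded from DLTs (Protocol 3.2.3), and the SRC reviews safety data as they accrue. The SAP's outputs come after database lock (SAP 7.4).
- *Cause of death is already available for every death.* Protocol 9.1.6 documents it as an AE outcome. The long-term follow-up calls mention only survival status.

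**Conclusion.** The concern holds for the on-treatment summary. Followed as written, SAP 15.1 undercounts a primary safety endpoint. On-treatment deaths from clear progression are missing from its on-treatment and all-death counts. Later deaths from progression, or from events starting more than 30 days after the last dose, are missing from its post-treatment and all-death counts. SAP 19 does not disclose the departure.

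The conclusion assumes that sites apply Protocol 9.1.1 as written and that the outputs follow the TEAE heading literally. The size cannot be taken from the documents, and the values of f above are illustrations, not estimates. The consequence is confined to the final safety summary and the RP2D benefit-risk assessment. The change should be made before the outputs are programmed.

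**What to change.** In SAP 15:

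- Add a Safety Population table of on-treatment deaths from any cause, defined by date as in Protocol 10.5.4. Present it by dose level in Part 1, by tumor cohort in Part 2A, and by dose and tumor cohort in Part 2B.
- State explicitly that all deaths will be listed, rather than leaving this to the general statement in SAP 7.4.
- Split deaths by cause (progression, AE, other) only where the eCRF collects cause.
- Keep TEAEs leading to death as a separate table, and remove or relabel its all-death category.

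The cost is SAP wording, one table and one explicit listing. The count by date needs no new data, because the SAP's OS and date-imputation rules already use the dates of first dose, last dose and death. The split by cause first needs a check of the eCRF, particularly for deaths learned of in long-term follow-up. If the sponsor prefers TEAE deaths only, SAP 19 should record that as a departure from the protocol.
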